3. A monthly urine pregnancy test must be performed by all women of child-bearing potential between the three monthly visits at the investigational site. Urine pregnancy tests may be performed at the investigational site or at home. Test results performed at home should be recorded in a patient diary and brought to each scheduled visit for the site to review. If a test result indicates a pregnancy, the patient must contact the investigator immediately.
4. Only required for Early Discontinuation due to lack of response / loss of response.
5. Same tube will be used for RQ PCR CCI [REDACTED]
6. For patients who are not in MMR at week 48 and for patients losing the response after week 48 assessments up to week 108 and who may benefit from a dose escalation, CCI [REDACTED].
7. Samples to be collected before first dose and 2 to 4 hours post dose.
8. After week 48, the ECG assessments will be done at week 60, week 84, week 108 and week 132 for patients on standard dose (80mg q.d. and 40mg b.i.d.).
9. For patients with dose escalation ECG assessment to be conducted: at dose escalation visit (pre-dose and two hours post-dose), two weeks post-dose escalation, 3 months post-dose escalation, 6 months post-dose escalation, 6 monthly thereafter. Please refer to [Section 8.4.3](#) for more information.
10. Personal and family history of the following conditions: Coronary artery disease, Hyperlipidaemia, Type 1 diabetes mellitus, Type 2 diabetes mellitus, Hypertension, medication taken for hypertension, Myocardial infarction or Cerebrovascular accident will be collected at screening. History of smoking, physical activity and diet will be collected at screening and end of treatment.
11. Week 24 echocardiogram can be performed within a window of +/- 4 weeks of the visit
12. After week 48, PRO assessment will be done every 24 weeks up to week 120 (i.e. these assessments will be completed at week 72, week 96 and week 120).
13. Safety follow-up may be done on site or via phone call with patient. The safety follow-up to be completed 30 days from the last dose of study treatment.

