- In the event of disease progression, the patient must be discontinued from the study treatment. The following events are considered disease progression.
 - CML-related death (any death during treatment or follow-up if the principal cause of death is marked as “study indication” in the eCRF by the investigator, or if the death occurred subsequent to documented progression to AP/BC and the cause of death is reported as “unknown” or not reported by the investigator)
 - Accelerated phase (AP) as defined by any of the following:
 - $\geq 15\%$ blasts in the peripheral blood or bone marrow aspirate, but $< 30\%$ blasts in both the peripheral blood and bone marrow aspirate
 - $\geq 30\%$ blasts plus promyelocytes in peripheral blood or bone marrow aspirate
 - $\geq 20\%$ basophils in the peripheral blood
 - Thrombocytopenia ($< 100 \times 10^9/L$) that is unrelated to therapy
 - Blast crisis (BC) as defined by any of the following:
 - $\geq 30\%$ blasts in peripheral blood or bone marrow aspirate
 - Appearance of extramedullary involvement other than hepatosplenomegaly proven by biopsy (i.e., chloroma).

Any value of AP or BC within the first 4 weeks of study treatment is not defined as progression to AP/BC within the study unless the subject discontinues study treatment due to progression.

If discontinuation from study treatment occurs, the investigator should make a reasonable effort to understand the primary reason for the participant’s premature discontinuation of study treatment and record this information.

Participants who discontinue from study treatment agree to return for the end of treatment and follow-up visits indicated in the Assessment Schedule (refer to [Section 8](#)).

If the participant cannot or is unwilling to attend any visit(s), the site staff should maintain regular telephone contact with the participant, or with a person pre-designated by the participant. This telephone contact should preferably be done according to the study visit schedule.

After discontinuation from study treatment, at a minimum, in abbreviated visits, the following data should be collected at clinic visits or via telephone/email contact:

- New / concomitant treatments
- Adverse Events / Serious Adverse Events

The investigator must also contact the IRT to register the participant's discontinuation from study treatment.

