1.1 Study design

The study is an international, multi-center, non-comparative, phase IIIb, treatment optimization study of asciminib (randomized 1:1 to either 40 mg b.i.d. or 80 mg q.d.) in adult subjects previously treated with 2 or more TKIs. 156 subjects will be randomized to either asciminib 40 mg b.i.d. or 80 mg q.d. An additional 30 subjects (randomized to either asciminib 40 mg b.i.d. or 80 mg q.d.) intolerant only to last TKI and in MMR at baseline will also be included.

Randomization is only used to have a balance in the allocation of treatment into either asciminib 40 mg b.i.d. or 80 mg q.d. The trial will not be powered to compare both treatments.

In subjects not achieving MMR at 48 weeks or losing the response after the week 48 assessment up to week 108, asciminib dose may be escalated to 200 mg q.d. if in the investigator's opinion

the subject may benefit from the escalation. In addition, there must not be any grade 3 or 4 toxicity while on therapy, or persistent grade 2 toxicity, possibly related to asciminib and unresponsive to optimal management.

[figure not shown]
BCR::ABL1 and **CCI** results are required before increasing asciminib dose, therefore the dose escalation can occur at next scheduled visit upon results review of the prior visit. In subjects losing response after the week 48 assessment, the last possible time point to initiate the 200 mg dose will be the week 120 visit to ensure that efficacy and safety of the dose escalation can be sufficiently established during the remaining trial follow up period.

If a dose decrease is required, subjects will return to the initial dosing regimen (q.d. or b.i.d.) they were using before the dose increase which was considered tolerable. For this reason, if a subject escalates from 40 mg b.i.d. to 200 mg q.d., in case of a required dose decrease, use of 80 mg q.d. is not allowed and the subject will continue 40 mg b.i.d. asciminib.

All subjects will be treated for a maximum duration of 144 weeks.

The primary endpoint of the study is MMR at 48 weeks.

Figure 1-1 Study design

*Treatment assignment to 40 mg b.i.d. or 80 mg q.d. (1:1) will be done through Interactive Response Technology (IRT).

Three analyses are planned for this study, including the 48-week primary analysis, the 96-week analysis, and the End-of-Study-Treatment (EOsT) analysis. The timing when those analyses are conducted is summarized in Section 2.1.

No formal interim efficacy analysis is planned in this study.

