Subjects in FAS will be categorized with counts and percentages provided for cytogenetic response at week 48 and EOT. Shift tables will also be employed to examine the changes in cytogenetic response category from baseline.

CCyR rates at Weeks 48 and EOT and the associated 95% confidence intervals based on the Clopper-Pearson method will be presented.

TTF, PFS and OS

For each endpoint the survival distribution will be estimated using the Kaplan-Meier method, and Kaplan-Meier curves, medians and 95% confidence intervals [[Brookmeyer and Crowley](#)

[1982](#)] of the medians, along with the proportion of subjects who have not experienced the respective events at 1, 2 and 3 years and the associated 95% confidence intervals, will be presented.

TTF: For subjects in the FAS who have not reached treatment failure, their TTFs will be censored at the time of their last study assessment (PCR, cytogenetic, hematologic or extramedullary) before the cut-off date.

PFS: For subjects who have not experienced an event (disease progression to AP/BC or death from any cause), their PFS times will be censored at the date of last study assessment (PCR, cytogenetic, hematologic or extramedullary) before the cut-off date.

OS: Subjects who are alive at the time of the analysis data cutoff date will be censored at the date of last contact (see [Section 2.1.1](#)) before the cut-off date.

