2.13 Interim analysis

No formal interim analysis is planned for this trial. The following analyses are planned as detailed below.

- 48-week primary analysis: Formal testing of the primary endpoint will be performed. Analyses of other efficacy endpoints at and by week 48 and safety analyses will also be performed.
- 96-week analysis: Analyses of efficacy endpoints at and by week 96 and safety analyses will be performed.
- End of study treatment analysis similar to the 96-week analysis without formal statistical testing. All efficacy and safety analyses will be included.

3 Sample size calculation

A sample size of 156 subjects (randomized to either asciminib 40 mg b.i.d. or 80 mg q.d.) will have 80% power to reject the null hypothesis proportion of 23% (upper limit of 95% exact binomial CI of the MMR rate at Week 48 in Bosutinib arm in ASCEMBL: see below) at 0.025 one-sided level of significance if the true rate (under alternative hypothesis) is 33% (considering a clinically meaningful difference of 10% or more) using exact test for single proportion (nQuery 7).

The MMR rate (95% CI) at Week 48 in Bosutinib arm of ASCEMBL trial (at ASCEMBL study Week 24 primary CSR (Data cut-off date of 25-May-2020, Table 14.2-1.1.1)) was 11.1 % (4.2% – 22.6%); 54 subjects were eligible for this sample size computation.

An additional 30 subjects based on medical justification (randomized to either asciminib 40 mg b.i.d. or 80 mg q.d.) intolerant only to last TKI and in MMR at baseline will also be analyzed.

4 Change to protocol specified analyses

Not applicable.

5 Appendix

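### OS and PFS are to be estimated at 1, 2 and 3 years, but vital status and AP/BC are neither required nor scheduled beyond 30 days after the last dose; both are likely overstated, by an amount the documents do not allow us to derive

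*SAP*

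**What the plan says.** **Endpoints.** SAP 2.6.1.3 counts OS from randomization to death, and PFS from randomization to AP/BC or death from any cause. SAP 2.6.2 gives both Kaplan-Meier curves, medians and event-free proportions at 1, 2 and 3 years.

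**Censoring.** The OS rule is "OS: Subjects who are alive at the time of the analysis data cutoff date will be censored at the date of last contact". The last-contact sources in SAP Table 2-4 include no survival-status form. For PFS, SAP 2.6.1.3 censors at the last study assessment or the last post-treatment follow-up, while SAP 2.6.2 names only the last study assessment.

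**Length of observation.** SAP 1.1: "All subjects will be treated for a maximum duration of 144 weeks". Protocol Table 8-1, footnote 13: "The safety follow-up to be completed 30 days from the last dose of study treatment". Protocol Sections 8 and 9.3 give the same 30 days, and the table header shows no later column.

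**After stopping.** Protocol 9.1.1: "After discontinuation from study treatment, at a minimum, in abbreviated visits, the following data should be collected at clinic visits or via telephone/email contact". Two items follow: new or concomitant treatments, and AEs/SAEs.

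**What the SAP expects.** SAP 2.1.1 lets assessments after the end-of-treatment visit count for OS and PFS, and SAP 2.7.2 summarises post-treatment deaths. Neither document schedules the collection of such data.

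**The concern.** Kaplan-Meier is valid here only if patients who leave observation have the same later risk as those who remain. The protocol makes that doubtful. Under 9.1.1 disease progression obliges the patient to stop, and treatment failure should lead to stopping, with an exception for patients who have no alternative option. Leaving observation is therefore tied by rule to poor disease control.

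If later deaths and progressions are not sought in these patients, the curves mainly describe patients who stay on asciminib, yet they would be reported as survival of all patients treated. SAP 2.6.5 plans no sensitivity analysis for secondary endpoints that would expose the difference.

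**Working it through.** **1. The plan's own figure.** No event count, power or precision is given for OS or PFS. The only design figure is the 80% power for the primary endpoint in SAP Section 3, based on n = 156, a null rate of 0.23, an alternative of 0.33 and a one-sided level of 0.025. The smallest r with P(X ≥ r | 0.23) ≤ 0.025 is 47. The exact one-sided level is 0.0241 and the power at 0.33 is 0.801. The figure reproduces, and nothing below changes it.

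**2. Routes by which a later event could be recorded.**

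| Route | Reach beyond 30 days after the last dose |
|---|---|
| Scheduled visits (Protocol 8, Table 8-1, 9.3) | None visible |
| Contacts after discontinuation (9.1.1) | Telephone contact for patients who do not attend, preferably on the visit schedule; neither vital status nor AP/BC is a listed item |
| SAE reporting (10.1.4) | Only if a causal relation to treatment is suspected |
| Progression or death from progression as an SAE (10.1.1) | Excluded unless considered treatment-related |
| Last-contact date (SAP Table 2-4) | Later antineoplastic therapy dates can extend OS follow-up; no survival form |

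A CML death six months after stopping thus has no required path into the database unless treatment is suspected.

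**3. Longest scheduled observation.**
- 144 × 7 + 1 + 30 = 1,039 days; 1,039 / 365.25 = 2.84 years.
- With both +7-day windows: 1,053 / 365.25 = 2.88 years.
- Three years: 3 × 365.25 = 1,095.75 days.

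No patient has scheduled observation at 3 years. This needs no assumption about hazards.

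**4. How many might leave early.** The benchmark is the asciminib arm of the earlier phase III study against bosutinib (Protocol 1.1): 37.6% discontinued, at a median follow-up of 14.9 months.
- 156 × 0.376 = 58.7, about 59 patients.
- Constant hazard, treating 14.9 months as a fixed time: λ = −ln(1 − 0.376) / 14.9 = 0.0317 per month.
- By 24 months: 1 − exp(−24λ) = 0.532, about 83 of 156.

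**5. Illustration of the bias at 2 years.** Assumptions: on-treatment death hazard h of 1% or 2% per year; hazard kh after stopping; stopping hazard λ from step 4; censoring one month after stopping. The documents give neither h nor k.
- True survival: S(t) = exp(−(h+λ)t) + ∫₀ᵗ λ exp(−(h+λ)s) exp(−kh(t−s)) ds.
- Kaplan-Meier limit: exp(−∫₀ᵗ [hO(u) + khR(u)] / [O(u) + R(u)] du), where O is the proportion alive on treatment and R the proportion alive who stopped within the last month.

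| h per year | k | True 2-year OS | Kaplan-Meier | Overstatement |
|---|---|---|---|---|
| 1% | 1 | 98.0% | 98.0% | 0 |
| 1% | 3 | 96.9% | 97.9% | 1.0 point |
| 1% | 5 | 95.7% | 97.8% | 2.0 points |
| 1% | 10 | 93.1% | 97.5% | 4.4 points |
| 2% | 1 | 96.1% | 96.1% | 0 |
| 2% | 3 | 93.9% | 95.9% | 2.0 points |
| 2% | 5 | 91.7% | 95.6% | 3.9 points |
| 2% | 10 | 86.9% | 95.0% | 8.1 points |

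Differences are taken from unrounded values.

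**The case against.** Censoring OS at last contact is the usual rule and is not wrong in itself; the gap lies in what is collected. OS and PFS are secondary, untested, and belong to a non-comparative study. Both points stand, and they limit the weight of this one.

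Four stronger readings are tempting, and the documents do not support them.

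- **That nothing is collected after stopping.** The 9.1.1 list is a minimum and includes AEs and SAEs. Contact may be with a person the patient has named, and later therapy dates can extend OS follow-up. What can be said is that vital status and AP/BC are not required or scheduled after day 30.
- **That all of the roughly 59 early stoppers are wrongly censored.** Deaths on treatment are already events for both endpoints, and AP/BC that causes the stop is already a PFS event. The PFS problem concerns patients who stop for other reasons; for OS it includes those who stop because of AP/BC. The benchmark population was also selected by ELN 2013 failure criteria, and Protocol 4.2 expects less advanced disease here.
- **That missed deaths divided by 156 give the bias.** If 5-15% of the 59 died later (an assumption without a source), that would be 3 to 9 deaths, or 2 to 6 points. This counts censored patients as survivors, whereas Kaplan-Meier gives them the later risk of those still observed. A rough correction is (59/156) × (p − q), with p the later death risk of those who stop and q that of those who stay. With q = 3% (assumed), p = 5% gives 0.8 points and p = 15% gives 4.5. If p = q the bias is zero.
- **That upward bias is proven.** It is likely, given the stopping rules. If deaths reach the sponsor ad hoc while survivors' contact dates are not updated, it could run the other way.

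**Conclusion.** The point holds as a limit on what OS and PFS can show. Two parts rest on the documents alone: no one is required to ascertain vital status or AP/BC beyond 30 days after the last dose, and scheduled observation ends at 2.84 years (2.88 with windows), before the 3-year landmark. The different PFS censoring rules in SAP 2.6.1.3 and 2.6.2 add a smaller ambiguity.

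Informative censoring is an inference from the stopping rules, and overstatement is its likely result. The range of about 1 to 8 points at 2 years is illustrative. It depends on the assumed hazards and on the constant stopping rate extrapolated from the earlier study. One caveat applies: Table 8-1 is incomplete in the text available, so a survival item at the safety visit itself cannot be excluded, although no later visit is visible. The primary MMR analysis is untouched.

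**What to change.** **Preferred.** Add two items to the minimum post-discontinuation data in Protocol 9.1.1: vital status with date, and any AP/BC diagnosis, with date, known from routine care. Collect them up to each patient's Week-144 date, for patients who have not withdrawn consent. Reported AP/BC has to come from routine care because its definition rests on blood counts, marrow or biopsy, which a telephone question cannot establish. The cost is a protocol amendment with ethics approval, the corresponding eCRF fields and some site contact time; no new procedure is needed.

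**If collection cannot change.** State in SAP 2.6 that OS is observed to about 30 days after the last dose unless later contact is recorded, and that PFS is observed to the last on-study disease assessment. A single label of on treatment plus 30 days would misdescribe PFS. Do not present the landmark estimates as patient survival rates. This costs SAP text only.

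**In either case.** Drop the 3-year landmark, which follow-up to Week 144 would not reach either (144 × 7 / 365.25 = 2.76 years), and use one PFS censoring rule in SAP 2.6.1.3 and 2.6.2. The sample size of 156 and the stated power do not change.

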2.6.3 Handling of intercurrent events

Not applicable.

2.6.4 Handling of missing values not related to intercurrent event

Not applicable.

2.6.5 Sensitivity analyses

Not applicable.

2.6.6 Supplementary analyses

Not Applicable.

2.7 Safety analyses

For all safety analyses, the Safety set (SAF, SAF 2) will be used, except where stated otherwise.

Safety summaries (tables, figures) include only data from the on-treatment period with the exception of baseline data which will also be summarized where appropriate (e.g. change from baseline summaries). In addition, a separate summary for death including on treatment and post treatment deaths will be provided. In particular, summary tables for adverse events (AEs) will summarize only on-treatment events, with a start date during the on-treatment period (treatment-emergent AEs).

The overall observation period will be divided into three mutually exclusive segments:

1. Pre-treatment period: from day of participant's informed consent to the day before first dose of study medication
2. On-treatment period: from day of first dose of study medication to 30 days after last dose of study medication
3. Post-treatment period: starting at day 31 after last dose of study medication.

The following will also be summarized for a) **all** subjects using combined sets (SAF and SAF 2), for b) SAF 2 only, for c) subjects by dose escalation status (with or without dose escalation) and for d) only for subjects with dose escalation (prior to and after dose escalation):

- All deaths
- Serious adverse events and adverse events of special interest
- Adverse events leading to treatment discontinuation
- Grade 3 and 4 adverse events

Analysis of ECG data, for dose escalation is mentioned in [section 2.7.4.1](#).

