6.3.2 Instruction for prescribing and taking study treatment

- Asciminib should be administered in the fasted state: avoid food for at least 2 hours before the dose is taken and for at least 1 hour after the dose is taken. Water is permitted during this period.
- Asciminib should be taken with approximately 8 ounces (240 mL) of water.
- Asciminib should be swallowed whole and not chewed or crushed.
- If vomiting occurs within the first hour after taking the drug, re-dosing is allowed before the next scheduled dose.
- If the patient on q.d. regimen does not take asciminib within 12 hours after the approximate time of the usual dosing time, that dose should be skipped and treatment should continue with the next daily dose at the prescribed level.
- If the patient on b.i.d. regimen does not take asciminib within 6 hours after the approximate time of the usual dosing time, that dose should be skipped and treatment should continue with the next scheduled dose at the prescribed level.

Table 6-2 Dose and treatment schedule

Study treatments	Pharmaceutical form and route of administration	Target dose/ Daily dose	Use	Tablet Strength	Number of tablets	Regimen
Asciminib	Tablets for oral use	80 mg	Standard Dose	40 mg	1 tablet of 40 mg	b.i.d.
Asciminib	Tablets for oral use	80 mg	Standard Dose	40 mg	2 tablets of 40 mg	q.d.
Asciminib	Tablets for oral use	40 mg	Dose reduction for standard dose b.i.d.	20 mg	1 tablet of 20 mg	b.i.d.
Asciminib	Tablets for oral use	40 mg	Dose reduction for standard dose q.d.	40 mg	1 tablet of 40 mg	q.d.
Asciminib	Tablets for oral use	200 mg	Dose escalation from standard dose*	40 mg	5 tablet of 40 mg	q.d.
Asciminib	Tablets for oral use	80 mg	Dose reduction from 200mg q.d.**	40 mg	2 tablets of 40 mg	q.d.**

Study treatments	Pharmaceutical form and route of administration	Target dose/ Daily dose	Use	Tablet Strength	Number of tablets	Regimen
Asciminib	Tablets for oral use	80 mg	Dose reduction from 200mg q.d.**	40 mg	1 tablet of 40 mg	b.i.d.**

All kits of study treatment will be recorded via the IRT.

* Dose escalation may only occur based on investigators decision after week 48, from week 60 onwards and up to week 120 based on week 108 data.

** Patients on 200 mg q.d. needing a dose de-escalation will revert to 80 mg total daily dose of asciminib and will follow initial dosing schedule, either q.d. or b.i.d., as initially assigned by IRT.

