2.4 Treatments (study treatment, rescue medication, concomitant therapies, compliance)

2.4.1 Study treatment / compliance

The Safety set (SAF, SAF 2) will be used for the analyses below unless otherwise specified.

Duration of exposure, actual cumulative dose, average daily dose, dose intensity (DI) and relative dose intensity (RDI) will be summarized. Duration of exposure will be categorized into time intervals; frequency counts and percentages will be presented for the number (%) of subjects in each interval. The number (%) of subjects who have dose reductions or interruptions, and the reasons, will be summarized.

Subject level listings of all doses administered on treatment along with dose change reasons will be produced.

To summarize exposure data for treatment, this will be based on subjects in the corresponding Safety set with the date of last administration of study treatment and the date of first administration of study treatment.

Duration of exposure to study treatment

Duration of exposure to study treatment is considered by taking into account the duration of exposure to the investigational drug:

Duration of exposure to study treatment (weeks) = ((date of last administration of study treatment) – (date of first administration of study treatment) + 1) / 7.

The **duration of exposure in subject-years** is the total of the duration of exposure in years from all the subjects in the treatment.

The date of last administration of study treatment is defined in [Section 2.1.1](#).

Summary of duration of exposure to study treatment will include categorical summaries based on intervals (less than 24 weeks, at least 24 weeks, at least 48 weeks, at least 96 weeks) and continuous summaries (i.e. mean, standard deviation etc.).

Cumulative dose

Cumulative dose of a study treatment is defined as the total dose given during the study treatment exposure.

The **planned cumulative dose** for a study treatment refers to the total planned dose as per the protocol up to the last date of study treatment administration. The calculation for the study treatments is:

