2.7.1 Adverse events (AEs)

All the summary tables for adverse events (AEs) will be tabulated by randomized groups. AE summaries will include all AEs occurring during the on-treatment period. All AEs collected in the AE eCRF page will be listed along with the information collected on those AEs e.g. AE relationship to study drug, AE outcome, etc. AEs with start date outside of the on-treatment period will be flagged in the listings.

AEs will be summarized by number and percentage of subjects having at least one AE, having at least one AE in each primary system organ class (SOC) and for each preferred term (PT) using MedDRA coding. A subject with multiple occurrences of an AE will be counted only once in the respective AE category. A subject with multiple CTCAE grades or the same preferred term will be summarized under the maximum CTCAE grade recorded for the event. AE with missing CTCAE grade will be included in the 'All grades' column of the summary tables.

In AE summaries, the primary system organ class will be presented alphabetically and the preferred terms will be sorted within primary SOC in descending frequency. The sorting order for the preferred term will be based on their frequency in the asciminib 40 mg b.i.d. group.

The following adverse event summaries will be produced: overview of adverse events and deaths, AEs by SOC and PT, summarized by relationship, seriousness, leading to treatment discontinuation, leading to dose interruption/adjustment, requiring additional therapy, and leading to fatal outcome. The study treatment-related AEs/SAEs/AEs leading to treatment discontinuation as well as SAE with fatal outcome are summarized for the corresponding Safety set.

For posting to ClinTrial.gov and EudraCT, a summary table of on-treatment deaths and serious AEs and another summary table of non serious AEs, both including occurrences (an occurrence is defined as >1 day between start and prior end date of record of same preferred term) and sorted by SOC and PT, will be presented as well.

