2.7.1.1 Adverse events of special interest / grouping of AEs

Data analysis of AESIs

An adverse event of special interest (AESI) is a grouping of adverse events that are of scientific and medical concern specific to compound asciminib. These groupings are defined using

MedDRA terms, SMQs (standardized MedDRA queries), HLGTS (high level group terms), HLT (high level terms) and PTs (preferred terms). Customized SMQs (Novartis MedDRA queries, NMQ) may also be used. A NMQ is a customized group of search terms which defines a medical concept for which there is no official SMQ available or the available SMQ does not completely fit the need. It may include a combination of single terms and/or an existing SMQ, narrow or broad. The latest approved version of CRS (Case Retrieval Strategy) prior to the respective database lock will be used.

For each specified AESI, number and percentage of subjects with at least one event of the AESI occurring during the on-treatment period will be summarized.

Summaries of these AESIs will be provided (specifying grade, SAE, relationship, leading to treatment discontinuation, leading to dose adjustment/interruption, death, etc.). If sufficient number of events occurred, analysis of time to first occurrence will be applied.

A listing of all grouping levels down to the MedDRA PTs used to define each AESI will be generated.

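### AE summaries by dose escalation report only the percentage of subjects with an event, although time at risk differs between the groups and periods set side by side

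*SAP*

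**What the plan says.** SAP 2.7 lists four outcome groups: all deaths; SAEs and AESIs; AEs leading to treatment discontinuation; and grade 3 and 4 AEs. Besides the main safety sets, each is to be shown in two further splits. Split d) is described as "only for subjects with dose escalation (prior to and after dose escalation". Split c), which sets escalated and non-escalated subjects against each other over the whole on-treatment period, is described as "subjects by dose escalation status (with or without dose escalation".

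The measure comes from SAP 2.7.1: "AEs will be summarized by number and percentage of subjects having at least one AE". SAP 2.7.1.1 does the same for AESIs: "number and percentage of subjects with at least one event of the AESI occurring during the on-treatment period will be summarized". The one time-based AE analysis is also there: "If sufficient number of events occurred, analysis of time to first occurrence will be applied". It is conditional, limited to AESIs, and not tied to escalation status or period.

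On timing, the footnote to Protocol Table 6-2 allows escalation "from week 60 onwards and up to week 120 based on week 108 data", and SAP 1.1 states "All subjects will be treated for a maximum duration of 144 weeks". SAP 2.4.1 defines exposure in subject-years, which "is the total of the duration of exposure in years from all the subjects in the treatment", but no AE summary uses it as a denominator. The SAP specifies no exposure-adjusted AE rate, equal-length window, landmark or time-dependent escalation status.

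**The concern.** The percentage with at least one event grows with time at risk. Two columns with different observation times can differ with no difference in risk, or agree when risk has changed.

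Here the imbalance is built in. In d), the split between before and after is set by the escalation week. In c), an escalated subject must have stayed on treatment to at least Week 60, while the other group holds everyone who stopped earlier.

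Two rows in d) have a further problem. A subject who escalates has, by definition, neither died nor permanently discontinued before escalating. The before column for deaths is therefore zero by construction. The one for AEs leading to discontinuation is nearly so: only an event that began before escalation and led to stopping afterwards could fall there. Protocol 6.6.2 also makes escalation conditional on the absence of certain possibly related toxicity, including grade 3 or 4, so such events are selected against in the before column.

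What is at stake is how the escalated period is read. Protocol Section 3 sets the latest escalation at Week 120 so that enough follow-up remains to judge its efficacy and safety. The earlier 200 mg q.d. experience in Protocol 4.2 is 12 patients, 8 of them with grade 3 or higher AEs.

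**Working it through.** The documents give no figure on this point to reproduce, so the check derives the time at risk and then the percentages that it implies.

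**Inputs.** Escalation week w = 60 to 120 (Protocol Table 6-2 footnote). End of treatment at Week 144 (SAP 1.1). AE window to 30 days after last dose, or 30/7 = 4.29 weeks (SAP 2.7). For illustration, 50.6% of patients with grade 3/4 AEs in the asciminib arm of the earlier phase III trial (Protocol 1.1), with 43.4 weeks median exposure (Protocol 4.2).

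**Time at risk in d), for a subject completing 144 weeks.** Before = w; after = 144 − w, or 144 − w + 4.29 with the AE window.

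**Illustrative hazard.** h = −ln(1 − 0.506)/43.4 = 0.01625 per week, or 0.848 per year. Percentage with at least one event over t weeks = 1 − exp(−h·t), with the same h in both periods:

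| Escalation week | Weeks before / after | Ratio (with tail) | % before | % after (with tail) |
|---|---|---|---|---|
| 60 | 60 / 84 | 0.71 (0.68) | 62.3 | 74.5 (76.2) |
| 72 | 72 / 72 | 1.0 (0.94) | 69.0 | 69.0 (71.0) |
| 84 | 84 / 60 | 1.4 (1.31) | 74.5 | 62.3 (64.8) |
| 96 | 96 / 48 | 2.0 (1.84) | 79.0 | 54.2 (57.2) |
| 108 | 108 / 36 | 3.0 (2.68) | 82.7 | 44.3 (48.0) |
| 120 | 120 / 24 | 5.0 (4.24) | 85.8 | 32.3 (36.8) |

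The apparent direction reverses with the escalation week although risk never changes.

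**A doubled hazard after a Week 120 escalation.** 1 − exp(−2h·24) = 54.2% (60.1% with the tail), still below 85.8%. The hazard would have to rise 5.0-fold (120/24), or 4.24-fold with the tail, for the two percentages to be equal. Per 100 subject-years, the unchanged hazard is 84.8 in both periods and a doubled one is 169.6, whatever the escalation week.

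**Without the earlier-trial calibration.** Week 120 escalation, no change in risk:

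| Annual risk | % before (120 weeks) | % after (24 weeks) |
|---|---|---|
| 5% | 11.1 | 2.3 |
| 10% | 21.5 | 4.7 |
| 20% | 40.1 | 9.8 |
| 40% | 69.1 | 20.9 |

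**At the 96-week analysis.** The cut-off is 96 weeks after the last subject's first treatment (SAP 2.1). A last-enrolled subject who escalated at Week 84 has 84 versus 12 weeks (7-fold). Subjects enrolled earlier have more follow-up.

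**With versus without escalation, c).** Assume 10% annual risk in everyone, an escalated group followed for 144 weeks, and a share s of the other group stopping at Week 24 with the rest completing. Over 24 weeks, 1 − 0.9^(24/52.18) = 4.7%; over 144 weeks, 25.2%. The non-escalated percentage is s × 4.7% + (1 − s) × 25.2%. This gives 21.1% at s = 0.2, 17.5% at s = 0.376 (the discontinuation proportion in the earlier trial's asciminib arm) and 15.0% at s = 0.5, each against 25.2% in the escalated group. Both s and the stopping week are assumptions.

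**The case against.** The SAP says these outcomes are summarized. The study is non-comparative, and no test or between-period effect measure is planned. That stands: no error rate is affected and the primary endpoint is untouched. But a before/after layout has little purpose other than to be read across.

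The 5-fold gap is an extreme. Protocol 6.6.2 places escalation at Week 60 for subjects not in MMR at Week 48, where the times are 60 and 84 weeks and the distortion is modest. That also stands. The documents give no distribution of escalation weeks, so the net distortion in the pooled table cannot be stated in advance.

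The grade 3/4 illustration applies an all-cause hazard to subjects who can escalate only without certain possibly related toxicity. The before percentages are therefore probably higher than table d) would show. The calibration also treats a median exposure as everyone's exposure. Both criticisms are right, so the figures are not predictions; the annual-risk table shows the mechanism without that calibration.

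A reader might infer that these are the only safety data on 200 mg in the trial. The documents do not support that. SAP 2.7.4.1 repeats the ECG analyses by escalation status and before/after escalation, SAP 2.3.1 gives separate disposition tables for escalated subjects, and SAP 2.4.1 summarizes whether they remain on, complete or discontinue treatment.

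A reader might also infer that rates per subject-year would settle the matter. They would not. They correct unequal time, but not the structural zeros or the selection of who escalates. Escalated subjects may also return to 80 mg daily (Protocol 6.1.1), so time after escalation is not all time on 200 mg.

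**Conclusion.** The point holds for the AE summaries in c) and d). As planned, they cannot separate a change in risk from a difference in observation time. For completers, the before/after ratio runs from 0.71 (Week 60) to 5.0 (Week 120; 4.2 on the AE window). With an unchanged constant hazard, the illustrative percentages are 62.3% versus 74.5% at one end and 85.8% versus 32.3% (36.8% with the tail) at the other.

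The ratios follow from the documents. The percentages rest on a constant hazard, the stated calibration or annual risks, and no allowance for the toxicity condition. The 5-fold figure should not be carried over to c), for which the documents imply no such bound. There the problem is the guaranteed time on treatment of the escalated group.

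This is a worthwhile improvement to descriptive safety tables that are the main AE evidence on the escalated period. It is not a flaw in the primary analysis.

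**What to change.** In SAP 2.7:

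1. For SAEs, AESIs and grade 3/4 AEs in c) and d), add first-event rates per 100 subject-years with 95% confidence intervals beside the percentages. Split person-time at the escalation start date already defined in SAP 2.1.1. Within each period, end it at the first event, the end of the period or the data cut-off.
2. For c), restrict the non-escalated group to subjects still on treatment at Week 60 and count time from Week 60, or from escalation in the escalated group. Alternatively, treat escalation as a time-dependent status, which also uses late escalators' time between Week 60 and escalation.
3. For d), report deaths and AEs leading to discontinuation for the post-escalation period only. Footnote that death and discontinuation cannot precede escalation, and that related grade 3/4 events before escalation are selected against by the escalation condition. Label the columns as periods before and after escalation, not as doses.

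The cost is modest. The escalation date and subject-years are defined, and SAP 2.4.1 already divides exposure at escalation for the planned cumulative dose. Time to first event within each period is not yet derived and would need programming. Selection by response, tolerability and investigator judgement remains, so the tables stay descriptive.
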